3. OBJECTIVES AND ENDPOINTS

Table 3 Study objectives and endpoints (Amended, 21 August 2023)

Objectives	Endpoints
	Primary
Evaluate the safety profile of the Vi-CRM ₁₉₇ +O:2-CRM ₁₉₇ vaccine, with and without adjuvant.	
 • Percentage of participants with solicited administration-site events during 7 days after each vaccination, on the days of vaccination and the 6 subsequent days (study intervention administered on Day 1 and Day 169), per study group. • Percentage of participants with solicited systemic events during 7 days after each vaccination, on the days of vaccination and the 6 subsequent days (study intervention administered on Day 1 and Day 169), per study group. • Percentage of participants with unsolicited adverse events (AE) during 28 days after each vaccination, on the days of vaccination and 27 subsequent days (study intervention administered on Day 1 and Day 169), per study group. • Percentage of participants with any serious adverse event (SAE) from first vaccination until 28 days after second study intervention administration (Day 1 to Day 197), per study group. • Percentage of participants with AEs/SAEs leading to withdrawal from the study or withholding further study intervention administration, from first study intervention administration until 28 days after second study intervention administration (Day 1 to Day 197), per study group. • Percentage of participants with deviations from normal or baseline[†] values of haematological, renal, and hepatic panel test results at 7 days after each vaccination (Day 8 and Day 176), per study group.
	Secondary
Evaluate the long-term safety profile of the Vi-CRM ₁₉₇ +O:2-CRM ₁₉₇ vaccine, with and without adjuvant.	
 • Percentage of participants with any SAE from 28 days after second vaccination (Day 197) up to Day 337, per study group. • Percentage of participants with AEs/SAEs leading to withdrawal from the study from 28 days after second vaccination (Day 197) up to Day 337, per study group.

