4. STUDY DESIGN

4.1. Overall design

This is a Phase 1 observer-blind, controlled, self-contained, randomised, single-centre, dose-escalation study with 3 Steps (Step 1a, Step 1b, and Step 2). A total of 96 participants in 7 study groups, including 17 sentinel participants, are planned to be enrolled in the study. [Figure 1](#) shows a visual representation of the study design and [Table 4](#) shows a description of the study intervention groups.

An electronic case report form (eCRF) and a paper Diary will be used for data collection, which will include biological sampling (blood) and safety follow-ups.

The study design, the enrolment, and the monitoring procedures will follow GSK safety standards for FTIH clinical studies (Refer to Sections [8.2.2](#) and [10.1.5](#) for details on staggered vaccination, safety monitoring, and holding rules).

The primary completion date will be at Visit 6 (Day 197), 28 days after administration of the second study intervention (booster vaccination). An extended safety follow-up will be performed until 6 months after this second study intervention administration (Day 337) for collection of SAEs.

Figure 1 Study design overview

[figure not shown]

Table 4 Study groups, intervention, and blinding

Study groups	Number of participants	Age (Min-Max)	Study intervention(s)	Blinding	
				FSFV → IA 1*	IA 1* → LSLV)
Step 1a low dose without Alum	12	18 – 50 years	2 intramuscular vaccinations (Day 1 and Day 169) with low dose of Vi-CRM ₁₉₇ +O:2-CRM ₁₉₇ without Alum	Observer-blind	Single-blind*
Step 1a control	6		1 intramuscular vaccination (Day 1) with TYPHIM VI and 1 intramuscular vaccination (Day 169) with CCI [REDACTED]		
Step 1b low dose with Alum	12		2 intramuscular vaccinations (Day 1 and Day 169) with low dose of ADJ+Vi-CRM ₁₉₇ +O:2-CRM ₁₉₇ with Alum		
Step 1b control	6		1 intramuscular vaccination (Day 1) with TYPHIM VI and 1 intramuscular vaccination (Day 169) with CCI [REDACTED]		
Step 2 full dose without Alum	24		2 intramuscular vaccinations (Day 1 and Day 169) with full dose of Vi-CRM ₁₉₇ +O:2-CRM ₁₉₇ without Alum		
Step 2 full dose with Alum	24		2 intramuscular vaccinations (Day 1 and Day 169) with full dose of ADJ+Vi-CRM ₁₉₇ +O:2-CRM ₁₉₇ with Alum		
Step 2 control	12		1 intramuscular vaccination (Day 1) with TYPHIM VI and 1 intramuscular vaccination (Day 169) with CCI [REDACTED]		

FSFV = first subject first visit; IA = interim analysis; LSLV = last subject last visit

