9.4. Statistical analyses

9.4.1. Primary endpoint(s) (Amended, 21 August 2023)

[figure not shown]
Endpoint description	Analysis set	Statistical analysis methods
• Percentage of participants with solicited administration-site events during 7 days after each vaccination, on the days of vaccination and the 6 subsequent days (study intervention administered on Day 1 and Day 169), per study group	Solicited Safety Set	• Number and percentages of participants with at least one, any, and Grade 3 administration-site solicited AEs
• Percentage of participants with solicited systemic events during 7 days after each vaccination, on the days of vaccination and the 6 subsequent days (study intervention administered on Day 1 and Day 169), per study group	Solicited Safety Set	• Number and percentages of participants with at least one, any, and Grade 3 systemic solicited AEs
• Percentage of participants with unsolicited AEs during 28 days after each vaccination, on the days of vaccination and 27 subsequent days (study intervention administered on Day 1 and Day 169), per study group	Unsolicited Safety Set	• Number and percentages of participants with unsolicited AEs
• Percentage of participants with any SAEs from first vaccination until 28 days after second study intervention administration (Day 1 to Day 197), per study group	Exposed Set	• Number and percentages of participants with SAEs
• Percentage of participants with AEs leading to withdrawal from the study or withholding further study intervention administration, from first study intervention administration until 28 days after second study intervention administration (Day 1 to Day 197), per study group	Exposed Set	• Number and percentage of participants with AEs/SAEs leading to withdrawal from the study or withholding further study intervention administration
• Percentage of participants with deviations from normal or baseline t values of haematological, renal, and hepatic panel test results at 7 days after each vaccination Day 8 and Day 176 per study group*	Exposed Set	• Number and percentages of participants having haematological, renal, and hepatic abnormalities

[†]Baseline for post-first vaccination at Day 8 is Day 1 (can also be screening blood draw, if performed within 3 days of first vaccination), and baseline for post-second vaccination at Day 176 is Day 169.

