6.4.1. ATTRIBUTING EVENTS TO VACCINE DOSES

The dose relative to an event is the most recent study dose given to a participant prior to the start of a given event. For example, if the start date of an adverse event is between Dose 1 and Dose 2, the relative dose will be Dose 1.

If an event starts on the same day as a study dose, the relative dose will be derived from the additional information provided in the CRF using the contents of the flag indicating if the event occurred before or after vaccination. If ‘after vaccination’ is selected or if the selection is missing, the relative dose for the event will be the one administered on the start day of the event. If ‘before vaccination’ is selected, the relative dose for the event will be the dose prior to this one. Where applicable, the event will be classified as “pre-treatment”.

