13. MEDICATIONS

Medication usage coded using the WHO Drug Dictionary Version GlobalC3Mar22 will be listed for the exposed set.

‘Prior’ medications are medications which started and stopped prior to the first dose of study treatment.

‘Concomitant’ medications are medications which were taken during the treatment period, or specifically:

- o started after the first dose of study treatment or
- o started prior to the first dose of study medication and were continued after the first dose of study treatment

The percentage of participants using concomitant medications (any medication, any antipyretic and any antipyretic taken prophylactically, respectively) during the 7-day follow-up period and during the 28-day follow-up period will be summarized by group after each vaccination and overall.

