16.1. ADVERSE EVENTS

The analysis of solicited adverse event will be performed in the Solicited Safety Set. The percentage of participants with at least 1 administration site AE (solicited and unsolicited), with at least 1 systemic AE (solicited and unsolicited) and with any AE during the 7-day or the 28-day follow-up period, for each step, will be tabulated with exact 95% CI after each vaccination and overall. The same calculations will be performed for symptoms rated as grade 3 (severe). This combined analysis of solicited and unsolicited AEs will be performed on the Exposed Set as requested for public disclosure. Solicited events and unsolicited AEs will be coded by MedDRA.

The percentage of doses followed by at least 1 administration site AE and by at least 1 systemic AE will be tabulated, overall vaccination course, with exact 95% CI. The same computations will be done for Grade 3 AEs, any AEs considered related to vaccination, any Grade 3 AEs considered related to vaccination and any AEs resulting in a medically attended visit.

The percentage of participants/doses reporting each individual solicited administration site and systemic AE during the 7-day follow-up period will be tabulated with exact 95% CI as follows:

- Over the 2 doses, the percentage of participants with the symptom and its exact 95% CI.
- Over the 2 doses, the percentage of doses with the symptom and its exact 95% CI.
- At each study dose (visit), the percentage of participants with the symptom and its exact 95% CI.

Percentage of participants with at least one fever event will be reported per grade (as per protocol scale) and per 0.5°C cumulative increments as from $\geq 38^{\circ}\text{C}$ to $\geq 40^{\circ}\text{C}$

Solicited events ongoing after the observation period reported by maximum intensity will be left out of summary tables and only reported in solicited AE listings. Any solicited event with onset day greater than solicited period (i.e., 7 days) will be reported as unsolicited AE and will be included in unsolicited summary tables and listings.

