The analysis of unsolicited adverse event will be performed in the Unsolicited Safety Set. The verbatim reports of unsolicited symptoms will be reviewed by a physician and the signs and symptoms will be coded per the Medical Dictionary for Regulatory Activities (MedDRA), Version 25.0. Every verbatim term will be matched with the appropriate preferred term (PT). The percentage of participants with unsolicited AEs within 28 days after any doses with its exact 95% CI will be tabulated by group, step and by MedDRA preferred term. Similar tabulation will be done for Grade 3 unsolicited AEs, for unsolicited AEs that resulted in a medically attended visit, for Grade 3 and causally related unsolicited

Document: \\dccar2dnetvnasc01p-lan1.quintiles.net\cp_ops\PROJECTS\Glaxo SmithKline\GSK205480_HAB61752\SAP
Author: PPD Version Number: 1.0
Version Date: 25OCT2022

Template No: CS_TP_BS016 – Revision 7
Effective Date: 01Nov2021

Reference: CS_WI_BS005

AEs and for unsolicited AEs causally related to vaccination. These tabulations will include System Organ Class (SOC) and SOC/PT analyses.

The number of participants who experienced at least 1 SAE after any dose, from dose 1 until 28 days post second dose (Day 197) and from Day 198 until Day 337 will be reported by treatment.

The following summaries for COVID-19 infections will be presented:

- Number of participants with an AE of suspected, probable or confirmed assessment of COVID-19 infection
- Number of participants who had a COVID-19 diagnosis test performed and the number of participants with positive, negative or indeterminate results
- Incidence of COVID-19 as AEs and SAEs

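### SAP 16.1 reports unsolicited AEs only after any dose, and 16.1.1 only lists AEs leading to withdrawal or a withheld dose, so two primary safety endpoints would not be reported as the protocol defines them

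*SAP*

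**What the plan says.** **Unsolicited AEs.** Protocol Section 3 (Table 3) lists as a primary endpoint "Percentage of participants with unsolicited adverse events (AE) during 28 days after each vaccination", per study group. Protocol 9.4.1 repeats it as "Percentage of participants with unsolicited AEs during 28 days after each vaccination" and assigns it to the Unsolicited Safety Set. SAP 16.1 specifies: "The percentage of participants with unsolicited AEs within 28 days after any doses with its exact 95% CI will be tabulated by group". It then asks for similar tables for Grade 3, related, Grade 3 related and medically attended events.

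Elsewhere the SAP separates the doses explicitly. Concomitant medication use "during the 28-day follow-up period will be summarized by group after each vaccination and overall" (SAP 13). In SAP 16.1 the table of solicited and unsolicited events together "will be tabulated with exact 95% CI after each vaccination and overall", and individual solicited events get a row for each dose. Of the combined table the SAP says: "This combined analysis of solicited and unsolicited AEs will be performed on the Exposed Set as requested for public disclosure".

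**AEs leading to withdrawal or a withheld dose.** Protocol 9.4.1 makes this a primary endpoint (Day 1 to Day 197), and 9.4.2 makes withdrawal alone a secondary endpoint (Day 197 to Day 337). Both call for number and percentage per group on the Exposed Set. SAP 16.1.1 provides listings only, and identifies the events through an outcome variable on the AE page.

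SAP 3.3 declares no departure from the protocol.

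**The concern.** A participant counted in an any-dose row may have had the event after dose 1, after dose 2 or after both, so that row does not give the rate after each vaccination. The limitation is sharpest in the controls. They receive "1 intramuscular vaccination (Day 1) with TYPHIM VI and 1 intramuscular vaccination (Day 169) with" a tetanus-diphtheria-pertussis booster, so their final any-dose figure describes a sequence of two different vaccines and gives a rate for neither.

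The distinction matters to this programme. Protocol 2.3 names a single-dose vaccine as a goal, and the amendment 1 rationale says the second dose is studied as a booster in case one dose is not enough. Readers will want the unsolicited AE burden of the first and second injections separately.

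For AEs leading to withdrawal or a withheld dose, a listing leaves the reader to build a primary endpoint by hand, with no stated denominator and no split at Day 197.

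**Working it through.** The plan states no figure for this point, so the check is mainly a comparison of texts. The nearest stated figures, the detection probabilities in Protocol Table 14, reproduce in all 18 rows (for example 1 − 0.85^12 = 85.8% for n = 12) and are not in question.

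**1. What the described outputs give for unsolicited AEs.**

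| Output | Dose 1 alone | Dose 2 alone | Unsolicited alone |
|---|---|---|---|
| Unsolicited tables, SAP 16.1, final | no | no | yes |
| Combined table, SAP 16.1 | yes | yes | no, merged with solicited |
| Same unsolicited tables at first interim (SAP 4.3; Protocol 9.5.1) | Step 2: yes; Step 1: depends on the cut | no | yes |
| Same unsolicited tables at second interim | no | no | yes |

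SAP 4.3 generates all summary tables planned for the final analysis at the interims. At the first interim, Step 2 participants have had one dose, so their any-dose table is a dose-1 table. SAP 4.3 names the Exposed Set for interim safety tables, so the denominator may differ from the Unsolicited Safety Set.

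For Step 1 the cut can be read in two ways. The note under Protocol Table 1 suggests data up to each participant's Day 29. SAP 4.3 and Protocol 9.5.1 can be read as a calendar cut, at 28 days after the first vaccination in Step 2. The note to Protocol Table 10 allows safety evaluations #3 and #4 to fall close together. Evaluation #4 follows the second dose in Step 1a, so a calendar cut could include some Step 1 second-dose data.

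**2. How much an any-dose count leaves open.** Let x be the number with an event after any dose, and d1 and d2 the numbers after each dose, among participants who received both. Then 0 ≤ d1 ≤ x, 0 ≤ d2 ≤ x and d1 + d2 ≥ x, which gives (x + 1)(x + 2)/2 possible pairs. If d1 is known, d2 runs from x − d1 to x, which is d1 + 1 values.

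Illustrations with assumed counts and planned group sizes (Protocol Table 4), not predictions:
- Full-dose group, n = 24, x = 8, with d1 = 4 known from the interim: d2 is between 8 − 4 = 4 and 8, so five values fit. The ends are 4/24 = 16.7% (exact 95% CI 4.7 to 37.4) and 8/24 = 33.3% (15.6 to 55.3).
- Step 1 low-dose group, n = 12, x = 4, if dose 1 is not shown separately: 5 × 6/2 = 15 pairs fit. Either dose could be 0/12 (0 to 26.5) or 4/12 = 33.3% (9.9 to 65.1).
- Step 1 control group, n = 6, x = 2, under the same condition: 3 × 4/2 = 6 pairs fit.

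**3. AEs leading to withdrawal or a withheld dose.** The nearest SAP outputs are these:
- SAP 9 tabulates premature discontinuation by reason, on the Enrolled Set and without an AE-specific split at Day 197. Treatment discontinuations are listed; the only summary of stopping study treatment is for COVID-19 reasons.
- SAP 14 counts doses given, without reasons.

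Neither gives the number with a dose withheld because of an AE. One such participant is 1/6 = 16.7%, 1/12 = 8.3% or 1/24 = 4.2% of a group.

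**4. Identifying these AEs.** The outcome categories in Protocol 10.3.9.4 describe resolution, sequelae or death, and none denotes withdrawal or a withheld dose. The Schedule of Activities has a separate eCRF-documented item for AEs/SAEs leading to withdrawal. Protocol 7.1 and 7.2 record the primary reason for stopping the intervention or leaving the study.

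**The case against.** **The endpoint may only define collection windows.** On this reading, naming each vaccination fixes the two 28-day periods, and an any-dose percentage over both satisfies it. The method column in Protocol 9.4.1 gives no by-vaccination instruction for unsolicited AEs. The reading is possible but weaker. The solicited endpoints use the same construction, their method cells are equally silent, and the SAP still gave them a row for each dose.

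**The first interim already gives dose 1.** This stands for Step 2, including TYPHIM VI in the Step 2 controls, and Protocol 9.5.1 plans an interim CSR. A reader might infer that the study will never show an unsolicited AE rate after dose 1. The documents do not support that. The interim does not supply dose 2 for any group.

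**The templates may contain the outputs.** SAP 8 leaves the format and content of the tables to templates that were not available. By-dose columns or an n (%) table may be there. This limits the finding to what the SAP text specifies.

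**The withdrawal gap is mainly presentational.** With groups of 6 to 24, counts can be worked out from listings, and SAP 9 and 14 cover part of the ground. That is fair as to consequence, but it does not meet the number and percentage that the protocol requires.

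**The outcome variable may be a different field.** A reader might infer that the SAP's rule cannot find these AEs at all. That would equate its outcome variable with the protocol's outcome list, which is an assumption about an eCRF that cannot be seen. What stands is that the field needs naming. Nor would the recorded primary reasons suffice alone, since they are broad categories and could miss a contributing AE.

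**Conclusion.** The point holds as a mismatch in the reporting specification. Followed as written, the SAP text does not produce the unsolicited AE percentage after each vaccination, or the per-group number and percentage with AEs leading to withdrawal or a withheld dose. Both are primary endpoints. The secondary withdrawal endpoint for the follow-up period has the same gap. SAP 3.3 discloses none of this. The SAP is based on the protocol of 23 August 2022, but the amendment history shows no change to these endpoint definitions, so the version difference does not explain it.

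The missing unsolicited results are dose 2 in all seven groups and, if the first interim is a calendar cut, possibly dose 1 in the four Step 1 groups. The counts in the working are illustrations and assume that everyone received both doses.

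A reader might infer that safety information is lost or that dosing decisions are affected. Neither follows: the data are collected, the analyses are descriptive (Protocol 9.1), and decisions to proceed rest on the iSRC and SRT reviews (Protocol 8.2.2.1). The change should be made before the final analysis. The conclusion rests on the SAP text, because the templates and eCRF could not be checked.

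**What to change.** - **SAP 16.1:** tabulate unsolicited AEs and the Grade 3, related, Grade 3 related and medically attended subsets on the Unsolicited Safety Set, after vaccination 1, after vaccination 2 and overall. The attribution rule already exists in SAP 6.4.1: "The dose relative to an event is the most recent study dose given to a participant prior to the start of a given event". Use participants given that dose as the denominator, and label control columns by the vaccine given.
- **SAP 16.1.1:** add number and percentage per group on the Exposed Set for AEs/SAEs leading to withdrawal or a withheld dose (Day 1 to Day 197), and leading to withdrawal (Day 198 to Day 337, which matches the SAE split in SAP 16.1 and avoids counting Day 197 twice).
- **Identification:** state which eCRF field flags these AEs. Use the Schedule of Activities record of AEs/SAEs leading to withdrawal, cross-checked against the reasons recorded under Protocol 7.1 and 7.2.
- **Templates:** align them with this text.

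The cost is SAP wording, two extra columns in the unsolicited AE tables and one short table. No new data are needed.

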16.1.1. ADVERSE EVENTS LEADING TO DISCONTINUATION FROM STUDY OR FROM TREATMENT

Adverse events leading to permanent discontinuation from study and leading to discontinuation of study vaccine but continued further study procedures (safety or immunogenicity) will be identified by using the variable pertaining to outcome the Adverse Events page of the (e)CRF, and listed, separately. AEs leading to discontinuation from treatment will be listed.

16.1.2. SERIOUS ADVERSE EVENTS

Serious adverse events (SAEs) are those events recorded as "Serious" on the Adverse Events page of the (e)CRF, and will be listed.

16.1.3. DERIVATION

Adverse Event	Intensity grade	Parameter
Redness/swelling at administration site (greatest surface diameter in mm)	0	<25 mm.
	1 (Mild)	≥25 to ≤50 mm.
	2 (Moderate)	>50 to ≤100 mm.
	3 (Severe)	>100 mm.
Temperature ^a	0	<38.0°C.
	1 (Mild)	≥38.0°C to <38.5°C.
	2 (Moderate)	≥38.5°C to <39.0°C.

Document: \\dccar2dnetvnasc01p-lan1.quintiles.net\cp_ops\PROJECTS\Glaxo SmithKline\GSK205480_HAB61752\SAP
Author: PPD Version Number: 1.0
Version Date: 25OCT2022

Template No: CS_TP_BS016 – Revision 7
Effective Date: 01Nov2021

Reference: CS_WI_BS005

	3 (Severe)	≥39.0°C.
--	------------	----------

^aFever is defined as temperature ≥38.0°C/100.4°F

Grading of other solicited events not requiring derivation can be found in Table 20, Appendix 3 of the protocol.

16.2. SAFETY LABORATORY EVALUATIONS

Laboratory results will be included in the reporting of this study for Hematology and Biochemistry. A list of laboratory assessments to be included in the outputs is included in Appendix 9 of the protocol.

For each group and for each haematology and biochemistry parameter:

- The percentage of participants having hematology and biochemistry results below or above the local laboratory reference ranges versus baseline will be tabulated by treatment, timepoint and step.
- The percentage of participants with hematology and biochemistry results by grade versus baseline (visit 1 for first vaccination, Visit 4 for second vaccination) will be tabulated by treatment, timepoint and step.

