10.2.1. Protocol-required safety laboratory assessments

Table 17 shows the protocol-required safety assays, which will be performed by the local laboratory.

Table 17 Protocol-required safety laboratory assessments

Laboratory assessments	Parameters
Safety Screening laboratory assays	
Haematology	
 • Leukocytes (white blood cells [WBC]) • Erythrocytes (red blood cells [RBC]) • Haemoglobin • Haematocrit • Platelets • Eosinophils • Basophils • Neutrophils • Monocytes • Lymphocytes
Clinical chemistry	
 • Total bilirubin • Aspartic aminotransferase (AST) • Alanine aminotransferase (ALT) • γ-Glutamyl transferase (γ-GT) • Lactic dehydrogenase (LDH) • Alkaline phosphatase (AP) • Total proteins • Glucose (random glucose) • Blood urea (BU)* • Creatinine • Sodium • Potassium
Other Screening tests	
 • Hepatitis B surface antigen antibodies • Hepatitis C virus antibodies • HIV antibodies • Prothrombin time • Blood human chorionic gonadotropin (hCG) pregnancy test (for women of childbearing potential)
Pre/Post-vaccination safety laboratory assays (Visit 1, Visit 2, Visit 4, and Visit 5)	
Haematology	
 • Leukocytes (WBC) • Erythrocytes (RBC) • Haemoglobin • Haematocrit • Platelets • Eosinophils • Basophils • Neutrophils • Monocytes • Lymphocytes
Clinical chemistry	
 • Creatinine • AST • ALT • BU*
Other tests	
 • Urine hCG pregnancy test (as needed for women of childbearing potential; required at Visit 1 and Visit 4)

*BU will be converted to blood urea nitrogen for grading purposes. Refer to Section 10.9.

ALT=alanine aminotransferase; AST=aspartate aminotransferase; BU=blood urea; hCG=human chorionic gonadotropin; RBC=red blood cell; SAE=serious adverse event; ULN=upper limit of normal; WBC=white blood cell
NOTES:

All haematology assay outputs should be reported in absolute values.

All events of ALT $\geq 3 \times$ upper limit of normal (ULN) and bilirubin $\geq 2 \times$ ULN ($>35\%$ direct bilirubin) or ALT $\geq 3 \times$ ULN, which may indicate severe liver injury (possible Hy's Law), must be reported as an SAE.

10.3. Appendix 3: Adverse Events: definitions and procedures for recording, evaluating, follow-up, and reporting Definition of AE

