10.9. Appendix 9: Toxicity grading scale for safety laboratory assessment

Laboratory test	Grade 1	Grade 2	Grade 3	Grade 4
BUN – mg/dL	<23 – 26	>26 – 31	>31	Requires dialysis
Creatinine – mg/dL (female)	>1.1 – 1.7	>1.7 – 2.0	>2.0 – 2.5	>2.5 or requires dialysis
Creatinine – mg/dL (male)	>1.3 – 1.7	>1.7 – 2.0	>2.0 – 2.5	>2.5 or requires dialysis
Eosinophils – cell/mm ³	>500 – 1500	>1500 – 5000	>5000	Hypereosinophilic
Haemoglobin (female) – gm/dL	11.0 – <11.6	9.5 – <11	8.0 – <9.5	<8.0
Haemoglobin (female/male) – change from baseline value – gm/dL	Any decrease – 1.5	>1.5 – 2.0	>2.0 – 5.0	>5.0
Haemoglobin (male) – gm/dL	12.5 – <12.9	10.5 – <12.5	8.5 – <10.5	<8.5
Liver function tests – ALT, AST increase by factor	≥1.1 – 2.5 x ULN	>2.5 – 5.0 x ULN	>5.0 – 10 x ULN	>10 x ULN
Lymphocyte decrease – cell/mm ³	750 - <800	500 - <750	250 - <500	<250
Neutrophil decrease – cell/mm ³	1340	1000 - <1340	500 - <1000	<500
Platelet decrease – cell/mm ³	125 000 – <150 000	100 000 – <125 000	25 000 – <100 000	<25 000
WBC decrease – cell/mm ³	2500 – <3700	1500 – <2500	1000 – <1500	<1000
WBC Increase – cell/mm ³	>10 000 – 15 000	>15 000 – 20 000	>20 000 – 25 000	>25 000

Toxicity Grading scale for safety laboratory test results have been based on the US FDA Guidance for Industry [[U.S. Department of Health and Human Services](#), 2007] and adjusted in consideration of local normal ranges provided by the site. Parameters not included in the FDA grading scales will not be graded; their assessment will be based on laboratory normal ranges and medical judgement.

ALT=alanine aminotransferase; AST=aspartate aminotransferase, BUN=blood urea nitrogen; ULN=upper limit of normal, WBC=white blood cells

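### SAP 16.2 takes its list of laboratory outputs from the grading scale, not from the post-vaccination panel, so four haematology parameters could be missed in a primary safety endpoint

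*SAP*

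**What the plan says.** SAP 16.2 covers the haematology and biochemistry reporting. It gives no list of tests of its own and refers the reader to the protocol: "A list of laboratory assessments to be included in the outputs is included in Appendix 9 of the protocol". It then asks for two tabulations for each haematology and biochemistry parameter. One gives results below or above the local reference range versus baseline. The other gives results by grade versus baseline.

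The appendix it names is headed "10.9. Appendix 9: Toxicity grading scale for safety laboratory assessment". A note under that table says: "Parameters not included in the FDA grading scales will not be graded; their assessment will be based on laboratory normal ranges", together with medical judgement. SAP 16.2.1 carries the same rule.

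The tests to be done are listed in Table 17 of protocol 10.2.1, which belongs to Appendix 2. The relevant part is labelled "Pre/Post-vaccination safety laboratory assays (Visit 1, Visit 2, Visit 4, and Visit 5"). Its haematology entries are "Leukocytes (WBC) • Erythrocytes (RBC) • Haemoglobin • Haematocrit • Platelets • Eosinophils • Basophils • Neutrophils • Monocytes • Lymphocytes" and its chemistry entries are "Creatinine • AST • ALT • BU".

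The primary endpoint (protocol Table 3 and Section 9.4.1) is the percentage of participants with deviations from normal or from baseline in the haematological, renal and hepatic panels at Day 8 and Day 176. The stated method is "Number and percentages of participants having haematological, renal, and hepatic abnormalities".

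**The concern.** A grading scale and a test list do different jobs. The scale holds only analytes that have grade cut-offs. The endpoint concerns departures from normal or baseline across whole panels and does not depend on whether a grade exists. If the scale is used as the list of outputs, any ungraded test that was collected falls off the list, even though both documents say such tests are assessed against normal ranges.

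What is at stake is the content of a primary safety table in a first-in-human study. One programmer could take the cross-reference as the definition of the outputs and deliver tables for the Appendix 9 analytes only. Another could follow the next line and deliver the full Table 17 panel. Each could cite SAP 16.2 in support. The first result would report part of the haematology panel under an endpoint that names the panel without limit. It would also be an undeclared departure, because SAP 3.3 says nothing in the analysis differs from the protocol and SAP 17 names only comments as data not summarised or presented.

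**Working it through.** The plan states no count of its own to reproduce. The check is a comparison of two lists.

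**Step 1: post-vaccination parameters in Table 17 (protocol 10.2.1).** Only the part for Visits 1, 2, 4 and 5 is used; the longer screening panel is left out.
- Haematology: WBC, RBC, haemoglobin, haematocrit, platelets, eosinophils, basophils, neutrophils, monocytes, lymphocytes = 10.
- Chemistry: creatinine and blood urea (renal), AST and ALT (hepatic) = 4.
- Total: 10 + 4 = 14.

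**Step 2: distinct analytes in Appendix 9 (protocol 10.9).** The table has 13 rows.
- Creatinine has two rows (female, male): remove 1.
- Haemoglobin has three (female, male, change from baseline): remove 2.
- WBC has two (decrease, increase): remove 1.
- ALT and AST share one row: add 1.
- Result: 13 − 1 − 2 − 1 + 1 = 10. These are BUN, creatinine, eosinophils, haemoglobin, ALT, AST, lymphocytes, neutrophils, platelets and WBC.

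**Step 3: match the names.** Table 17 lists blood urea and Appendix 9 lists BUN. The Table 17 footnote links them: "BU will be converted to blood urea nitrogen for grading purposes". They count as the same parameter, so this is not an omission.

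**Step 4: take the difference.**

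| Panel | In Table 17 | Also in Appendix 9 | Absent from Appendix 9 |
|---|---|---|---|
| Haematology | 10 | 6 | 4 (RBC, haematocrit, basophils, monocytes) |
| Renal | 2 | 2 | 0 |
| Hepatic | 2 | 2 | 0 |
| Total | 14 | 10 | 4 |

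Share absent: 4/14 = 28.6% of the panel and 4/10 = 40% of haematology. Every Appendix 9 analyte is also in Table 17, so the mismatch runs one way only.

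**Step 5: set this against the rule for ungraded tests.** The four absent parameters are exactly the ungraded ones in the post-vaccination panel. If the outputs stopped at Appendix 9, the rule in SAP 16.2.1 that ungraded parameters are judged on normal ranges would have nothing in the post-vaccination outputs to apply to. The cross-reference and that rule cannot both be followed literally.

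**Step 6: see what else depends on the list.** The by-grade tabulation can only cover graded analytes, so it holds the same 10 under either reading. Holding rule 2c (protocol Table 11) takes its laboratory grades from Section 10.9, so it does not depend on the four.

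**The case against.** A reader might infer that the SAP confines the outputs to Appendix 9 and that the four parameters will therefore never be tabulated. The documents do not support that, for these reasons:

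- The sentence in SAP 16.2 has no word of restriction or exclusion. An omission has to be inferred from a cross-reference.
- The next line of the same section asks for the tabulations for each haematology and biochemistry parameter. On its natural meaning that covers all ten haematology tests.
- SAP 16.2.1 and the Appendix 9 note both provide for ungraded parameters. That is better evidence that no restriction was meant than evidence of one.
- SAP 3.3 declares no change from the protocol, so anyone resolving the doubt should follow the protocol's panels.
- SAP 8 leaves the format and content of the tables to templates that are not among the documents reviewed. Those templates may already list all 14 parameters.
- The safety consequences are limited even under the literal reading. Under protocol 8.3.2.1 the investigator still reviews every laboratory report and records clinically relevant changes as adverse events. The study is descriptive and tests no hypothesis.

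All of this stands, and it reduces the point from a loss of data to a risk of loss. It does not make the sentence right. The line about each parameter comes directly after the sentence saying which assessments are included, so it can also be read as each listed parameter. The SAP was written on the protocol of 23 August 2022 and the current protocol is Amendment 2 of 21 August 2023. The visible change tables record no change to Table 17 or Appendix 9, so the difference in versions does not explain the mismatch.

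**Conclusion.** The point holds as an internal inconsistency of minor severity. SAP 16.2 cites the wrong appendix for its list of laboratory outputs. The cited table covers 10 of the 14 post-vaccination parameters, and the four it lacks are all haematology. Read literally, the reference could remove them from the reference-range tabulation at both Day 8 and Day 176, for a primary safety endpoint that is not limited to graded tests.

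The figure of 4 in 14 measures the mismatch between the two lists. It is not an established loss from the report. It becomes a loss only if the cross-reference is taken as the full definition of the outputs and the templates follow it, and the documents available do not show that. Nor do they support calling this a deliberate choice to analyse ten parameters. The count rests on two assumptions: blood urea and BUN are one parameter, and the pre/post-vaccination part of Table 17 is the panel that the endpoint means.

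**What to change.** In SAP 16.2, replace the reference to Appendix 9 as the list of outputs. State that the below/above reference-range tabulation covers all 14 parameters in the pre/post-vaccination part of protocol Table 17 (Section 10.2.1), and that the by-grade tabulation covers the 10 analytes graded in Appendix 9. Then check that the table templates match.

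The cost is one sentence and four more parameters in the reference-range table. The data are already collected under the protocol. The edit can go into the same update that aligns the SAP with the current protocol amendment.
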